## 4.1.4 Drug assignment and administration of doses for each trial participant

Trial medication will be dispensed at the investigational sites in accordance with the Flow Chart. At dispensing visits trial participants will be given the appropriate number of medication kits for BI 685509 (range 1-2) depending on the interval between the visits (for further kit details refer to Section 4.1.6). The last dose of BI 685509 will be administered in the evening of the day before the EoT visit.

All trial participants, regardless of the treatment group they are assigned to, will start at Visit 2 on a dose of BI 685509 BID or matching placebo. At Visit 3, 7 days later, and again at Visit 4, a further 7 days after Visit 3, all trial participants will be up-titrated first to a dose of BI 685509 BID or matching placebo, and then to a dose of BI 685509 BID or matching placebo. In this way the blind across treatment groups will be maintained (refer to Table 4.1.4: 1). Trial participants will be informed about the dose titration period and will be made aware that up-titration for BI 685509 is being used. If a trial participant does not tolerate an up-titration, e.g. due to orthostatic dysregulation, the rules in Section 4.1.4.1 must be followed. From Visit 4 onwards, trial participants will continue to receive the maximum dose of 3mg BI 685509 BID (unless a down-titration is required), until reaching the EoT visit 8 weeks after starting the trial medication.

If a trial participant has an AE that, based on Investigator judgement, may be related to BI 685509, the trial medication can either be:

• interrupted (i.e. the trial medication is stopped, and subsequently re-started. The uptitration approach described above is followed.)

OR

• the dose can be reduced (down-titrated) for BI 685509 if the trial participant has successfully completed the dose titration period (i.e. Visit 4).

For further details refer to Sections 4.1.4.1 and 4.1.4.2.

All trial medication assignments, including up / down-titrations for BI 685509 and provision of replacement kits, will be managed through the IRT system. Down-titrations of BI 685509 must not be performed by instructing the trial participant to take less than the two daily doses (refer to Section 4.1.4.1).

Page 46 of 98

Proprietary confidential information © 2023 Boehringer Ingelheim International GmbH or one or more of its affiliated companies

Pandomisation Allocation	Week 1 of Treatment	Week 2 of Treatment	Week 3 of Treatment Onwards
Kandonnsation Anocation	Dispensed at Visit 2	Dispensed at Visit 3	Dispensed at Visit 4 onwards
Treatment group 1 (BI 685509 BID)	BI 685509	BI 685509 (Up-titration)	BI 685509 (Up-titration)
Treatment group 2 (Placebo to BI 685509)	BI 685509 matching placebo	BI 685509 matching placebo (Up-titration)	BI 685509 matching placebo (Up-titration)

Table 4.1.4: 1Drug assignment and dosage by treatment group

From the start of the treatment period (i.e. from Visit 2), and until reaching the EoT visit 8 weeks later, trial participants will be instructed to take BI 685509 orally twice a day (BID). Each dose of BI 685509 will consist of one film-coated tablet. It is recommended that the first daily dose is taken in the morning, and the second dose in the evening. Ideally there should be at least 10 hours in between the intake of each dose. BI 685509 should be taken at approximately the same time every day. If a dose is missed this must not be rectified by taking two doses (i.e. double doses) at the next time point; if a dose is missed by more than 6 hours, that dose should be skipped altogether and the next dose taken as scheduled. Also refer to Section 4.1.4.2 for further details regarding interruption of trial medication. Trial medication should be taken with a glass of water and can be taken with or without food. In the morning of a visit, the trial medication will be administered as part of the visit. Therefore, on these days, trial participants should be instructed not to take their morning dose in advance of the visits.

participants who fail to follow these instructions should have the visit re-scheduled as soon as possible, ideally on the following day (refer to Section 6.1). On days with no scheduled visit the trial participant will self-administer their medication at home. Trial participants should be instructed to bring all unused trial medication and empty wallets / packaging with them when they return for clinic visits to the investigational site.

In case of a temporary interruption to treatment, refer to Sections 3.3.4.1, 4.1.4.1 and 4.1.4.2. In the event of force majeure or other disrupting circumstances (e.g. pandemic, war; refer to Section 6) physical trial participant visits to sites may not be feasible or may need to be restricted to ensure trial participant safety. Based on a thorough assessment of the benefits and risks, the Investigator may still decide to continue trial medication, and, if acceptable according to local law and regulations, trial medication may be shipped from the site to the trial participant's home.

#### 4.1.4.1 Rules for down-titration in case of intolerance to BI 685509

If a trial participant has an AE that, based on Investigator judgement, may be related to trial medication, the down-titration rules below must be followed. These rules apply if the trial participant has successfully completed the dose titration period (i.e. Visit 4) and is either still taking their final assigned dose of trial medication, or if they have missed  $\leq 3$  consecutive doses. If the trial participant has not successfully completed the dose titration period (i.e. Visit 4), down-titration is not permitted; in case of persistent AEs or severe effects, the trial participant must permanently discontinue treatment (refer to Section 3.3.4.1).

• if the trial participant is receiving BID BI 685509 the dose will be down-titrated one level to 2 mg BID BI 685509

Once down-titration has taken place, no further up-titration will be permitted. If a trial participant continues to have an AE, or a new AE develops, that based on Investigator judgement, may be related to trial medication, a second down-titration will be permitted:

• if the trial participant is receiving BID BI 685509 the dose will be down-titrated to BID BI 685509

Down-titration must not be performed by taking less than the two daily doses or by splitting tablets so that a whole tablet is not taken. Down-titration will be managed through the IRT system (refer to Section 4.1.4). After the successful completion of the dose titration period (i.e. Visit 4), in case of persistent AEs despite down-titration, or severe effects at any dose, permanent treatment discontinuation should be considered (refer to Section 3.3.4.1). Trial participants who are down-titrated will need to return to the investigational site to receive their continuing supply of trial medication, either at the next scheduled visit or via an unscheduled visit.

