4.1.4.2 Rules for re-starting up-titration in case of interruption of BI 685509

An interruption of BI 685509 may have an influence on the tolerability. Hence, if a trial participant has missed > 3 consecutive doses of trial medication for any reason (e.g. due to an AE, or for compliance reasons), the rules below will apply for the safety of the trial participant. If  $\leq$  3 consecutive doses of trial medication have been missed and there is no related AE, then the next dose of trial medication should be taken as scheduled.

- after an interruption of trial medication of >3 consecutive doses, the trial participant should re-start the dose titration period at BID BI 685509 / matching placebo
- before any further up-titration occurs the trial participant must have taken the preceding dose for at least 7 consecutive days. This applies throughout the treatment period
  - o this may mean that a trial participant due to be up-titrated at Visit 3 or 4 (as per Table 4.1.4: 1) is held at their current dose until their next scheduled visit. They could also be up-titrated at an unscheduled visit once this requirement is met
- if interruption occurs after Visit 4, subsequent up-titration will be allowed either at a scheduled visit or at an unscheduled visit

Trial participants with an interruption of trial medication will need to return to the investigational site to receive their continuing supply of trial medication, either at the next scheduled visit or via an unscheduled visit.

<sup>1 Footnote: One dose refers to an individual time point e.g. morning dose or evening dose.

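### The dosing rules do not say whether a participant who was down-titrated and then misses more than 3 doses may be up-titrated again, or to what level

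*Protocol*

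**What the plan says.** Three parts of the protocol bear on this.

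- **Section 4.1.4.1 (down-titration).** Dose reduction is open only to participants who have completed titration at Visit 4. The rules apply if the participant "is either still taking their final assigned dose of trial medication, or if they have missed" no more than 3 consecutive doses. One reduction takes the dose to 2 mg BID, and a second is possible if a related adverse event continues or a new one appears. Then: "Once down-titration has taken place, no further up-titration will be permitted".
- **Section 4.1.4.2 (restart).** This covers anyone who has missed more than 3 consecutive doses, and gives adverse events and compliance as examples of the reason. "after an interruption of trial medication of >3 consecutive doses, the trial participant should re-start the dose titration period". Also: "before any further up-titration occurs the trial participant must have taken the preceding dose for at least 7 consecutive days". And: "if interruption occurs after Visit 4, subsequent up-titration will be allowed either at a scheduled visit or at an unscheduled visit".
- **Section 4.1.4 (parent section).** On restarting after an interruption for an adverse event: "The uptitration approach described above is followed". On the maintenance dose: "trial participants will continue to receive the maximum dose of 3mg BI 685509 BID (unless a down-titration is required"), with no mention of a restart. On which rules to consult: "In case of a temporary interruption to treatment, refer to" Sections 3.3.4.1, 4.1.4.1 and 4.1.4.2, without ranking them.

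Section 4.2.2.1 adds another route: temporary use of a prohibited drug forces a stop, and the restart is referred to 4.1.4.2. Section 3.3.4.1 says that after a temporary discontinuation the drug should be restarted if this is medically justified, and refers to 4.1.4 for dose adjustments. The SAP does not address the question.

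**The concern.** Because down-titration is possible only after Visit 4, any interruption that follows one also falls after Visit 4. The participant is then covered both by the ban in 4.1.4.1 and by the permission in 4.1.4.2. The two give different doses:

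- Under the ban taken literally, a participant who tolerated 2 mg goes back to the starting dose after a two-day lapse and stays there to the end of treatment.
- Under the restart rule taken literally, the participant may be stepped back up to 3 mg, the dose that was reduced because of a possibly related adverse event. That is 3/2 = 1.5 times the reduced dose.

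Section 4.1.4 routes all dose changes through IRT, so one rule has to be programmed. The protocol does not say which. What is at stake is tolerability and dose in individual participants.

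**Working it through.** **Can the scope sentence of 4.1.4.1 separate the two rules?** It limits when a reduction may be made (on the assigned dose, or at most 3 doses missed). The ban itself runs forward from the reduction and has no end point. If one argued that it lapses after more than 3 missed doses, nothing would then cap the re-escalation. Either way the question stays open.

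**Timeline inputs**
- More than 3 missed BID doses means at least 4 doses, or 2 days.
- EoT is Day 57 ± 5, so Days 52-62 (Flow Chart). The last dose is on the evening before, so the last dosing day is L = EoT − 1 = 51 to 61 (56 nominal).
- Each step takes at least 7 days (4.1.4.2). For a restart on Day R with unscheduled visits, 2 mg starts on R + 7 and 3 mg on R + 14.
- Assumptions: the restart level is redacted and is taken as the starting dose, because the titration period is re-started. The middle step is taken as 2 mg, one level below the 3 mg maximum.

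**Formulas**
- Dosing days left = L − R + 1
- Days at 3 mg = L − (R + 14) + 1 = L − R − 13
- Latest restart that still reaches 3 mg: R = L − 14, which gives 1 day at 3 mg

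**Restart on Day 29, weekly unscheduled steps**

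| EoT day | L | Days left | 4.1.4.1: days at starting dose | 4.1.4.2: starting / 2 mg / 3 mg | Days on which dose differs | Latest R reaching 3 mg |
|---|---|---|---|---|---|---|
| 52 | 51 | 23 | 23 | 7 / 7 / 9 | 16 (70%) | 37 |
| 57 | 56 | 28 | 28 | 7 / 7 / 14 | 21 (75%) | 42 |
| 62 | 61 | 33 | 33 | 7 / 7 / 19 | 26 (79%) | 47 |

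**Restart on Day 29, scheduled visits only.** The next dispensing visit is Visit 6, nominally Day 43. This gives 14 days at the starting dose, then 2 mg from Day 43 to L: 9, 14 or 19 days for L = 51, 56 or 61. The 3 mg dose is not reached, because no drug is dispensed at EoT.

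**Early case (nominal EoT).** 3 mg from Day 15, reduced on Day 16, Days 17-18 missed, restart on Day 19. Weekly steps give 2 mg on Day 26 and 3 mg on Day 33, with 56 − 19 − 13 = 24 days at 3 mg. One participant can therefore meet both rules well within the 8 weeks.

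**Effect on the primary estimate.** Section 7.5 assumes a 20% HVPG reduction on active, 0% on placebo, SD 25% and 20 per group. If one active participant lost the whole assumed effect through being held at the starting dose, the arm mean would move by 20/20 = 1 percentage point. The standard error of an arm mean is 25/√20 = 5.6 points. One point is an upper limit per participant, since it assumes that the starting dose does nothing.

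**The case against.** **A specific rule can be read over a general one.** The ban is categorical and addressed to down-titrated participants, while 4.1.4.2 is general. Its bullet on interruptions after Visit 4 can be read as saying at which visits up-titration may happen, not as lifting a ban. That reading gives one answer: restart, then no re-escalation. It is tenable, so the two sections are not impossible to reconcile. But the protocol does not state it.

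**Safeguards exist.** The requirement of medical justification in 3.3.4.1 covers every interruption, so no restart is automatic. The same section asks for sponsor consultation when short-term use of a restricted drug is needed, and lets the investigator stop treatment at any time. Vital signs and ECGs are repeated 1 and 2 hours after dosing while up-titration is occurring and at the following visit (Flow Chart, footnote 21). Blood pressure is measured daily at home. All this stands, but none of it sets a dose limit.

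**Return to 3 mg is not shown to be unsafe.** A reader might infer that participants would be put back on a dangerous dose. The documents do not support that. Section 4.1.4 itself prescribes the standard up-titration after an interruption for an adverse event, and Section 3.2 says that titration improves tolerability. Section 1.2.3 reports that orthostatic intolerance in the earlier cirrhosis trial recovered during continued treatment. Related events of grade 3 or higher stop treatment under 3.3.4.1, so the events behind a down-titration are essentially grade 1-2.

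**Inconsistent dosing between sites cannot be inferred.** IRT should apply one algorithm to everyone, and its specification is not among the documents.

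**Conclusion.** The gap holds as a minor one. The current text bars up-titration for a down-titrated participant in one section and allows it in the next, with no exception, cap or order of precedence. In the Day 29 example with weekly steps, the two rules give different doses on 16 of 23 to 26 of 33 remaining days, depending on the EoT date.

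The case should be rare, because it needs a down-titration and then a lapse of at least two days within about six weeks. The documents give no rate for either event, so I put no expected number on it. The day counts rest on the assumed restart dose and the assumed 2 mg middle step.

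A reader might also infer a bias in the HVPG result. One affected participant moves the active mean by at most 1 point against a standard error of 5.6 under the planning assumptions, which is negligible. SAP Section 4 also records that no Week 8 HVPG was collected and that the HVPG analysis was dropped. The point concerns dosing and tolerability in the protocol as written, and any later protocol that reuses these rules.

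**What to change.** 1. In 4.1.4.1, replace the ban with: *no up-titration above the reduced dose will be permitted*.
2. In 4.1.4.2, add: *A participant down-titrated before the interruption re-starts at the starting dose and is re-titrated in steps of at least 7 days to no more than the reduced dose. If the interruption was due to an AE possibly related to trial medication at the reduced dose, the cap is one level lower (the second down-titration in 4.1.4.1), or discontinuation is considered.*
3. Program the same cap in IRT.

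The second sentence of item 2 is needed because a plain cap at the reduced dose would send a participant back to 2 mg after an event at 2 mg. For someone already reduced twice, the reduced dose is the lower of the two, and discontinuation is then the only further step.

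For a Day 29 restart capped at 2 mg, weekly steps give 7 days at the starting dose and then 23 − 7 = 16 to 33 − 7 = 26 days at 2 mg (21 nominal). This keeps the gradual re-exposure that 4.1.4.2 intends and the protection that 4.1.4.1 intends.

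The cost is two short wording changes and a small IRT change. A few participants would receive a somewhat lower dose than 4.1.4.2 alone would allow. No visits are needed beyond those 4.1.4.2 already permits.

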4.1.4.2 Rules for re-starting up-titration in case of interruption of BI 685509

An interruption of BI 685509 may have an influence on the tolerability. Hence, if a trial participant has missed > 3 consecutive doses of trial medication for any reason (e.g. due to an AE, or for compliance reasons), the rules below will apply for the safety of the trial participant. If  $\leq$  3 consecutive doses of trial medication have been missed and there is no related AE, then the next dose of trial medication should be taken as scheduled.

- after an interruption of trial medication of >3 consecutive doses, the trial participant should re-start the dose titration period at BID BI 685509 / matching placebo
- before any further up-titration occurs the trial participant must have taken the preceding dose for at least 7 consecutive days. This applies throughout the treatment period
  - o this may mean that a trial participant due to be up-titrated at Visit 3 or 4 (as per Table 4.1.4: 1) is held at their current dose until their next scheduled visit. They could also be up-titrated at an unscheduled visit once this requirement is met
- if interruption occurs after Visit 4, subsequent up-titration will be allowed either at a scheduled visit or at an unscheduled visit

Trial participants with an interruption of trial medication will need to return to the investigational site to receive their continuing supply of trial medication, either at the next scheduled visit or via an unscheduled visit.

<sup>1 Footnote: One dose refers to an individual time point e.g. morning dose or evening dose.

#### 4.1.5 Blinding and procedures for unblinding

#### 4.1.5.1 Blinding

Trial participants, investigators, central reviewers, and everyone involved in trial conduct or analysis or with any other interest in this double-blind trial will remain blinded regarding the randomised treatment assignments until the database is declared ready for analysis according to the sponsor's SOPs. Further details regarding the timepoint of unblinding the database for analysis are documented in the TSAP.

The access to the randomisation code will be kept restricted until its documented release per sponsor SOP.

The randomisation codes will be provided to bioanalytics before the last trial participant completes the trial to allow for the

Bioanalytics will not disclose the randomisation code or the results of their measurements until the trial is officially unblinded after the database lock (DBL).

specific data must be unblinded and the treatment information must

be made available to selected individuals (e.g. The unblinding procedure and logistics specific to this purpose will be provided in a separate document. It should be noted will be communicated to the project and trial team prior to DBL.

A DMC, independent from the Sponsor, will perform an unblinded safety evaluation at intervals specified in the DMC charter in order to ensure that trial participants are protected from potential harm (refer to Section 8.7). A trial independent statistician (iSTAT) will be assigned to prepare tables and listings as well as the summary reports for the DMC based on the agreed upon format and layout. Randomisation codes will be provided to the iSTAT. All information, including AEs, mortality, laboratory parameters, and decisions from hepatic injury adjudication will be provided in an unblinded fashion. This will be accomplished by using coded labels and by providing the DMC members with the decoding information separately, if needed.

4.1.5.2 Emergency unblinding and breaking the code

Emergency unblinding will be available to the Investigator via IRT. It must only be used in an emergency situation when the identity of the trial medication must be known to the Investigator in order to provide appropriate medical treatment or otherwise assure safety of trial participants. The reason for unblinding must be documented in the source documents and / or appropriate eCRF page. If a trial participant is unblinded by the Investigator, the trial participant has to be discontinued from the trial (refer to Section 3.3.4.1).

Due to the requirements to report Suspected Unexpected Serious Adverse Reactions (SUSARs), it may be necessary for a representative from BI's PV group to access the randomisation code for individual trial participants during trial conduct. The access to the

code will only be given to authorised PV representatives for processing in the PV database system and not be shared further.

#### 4.1.6 Packaging, labelling, and re-supply

The investigational medicinal products will be provided by Boehringer Ingelheim or a designated Clinical Research Organisation (CRO). They will be packaged and labelled in accordance with the principles of Good Manufacturing Practice. Re-supply to the sites will be managed via an IRT system, which will also monitor expiry dates of supplies available at the sites.

In this trial, each medication kit with BID BI 685509 will contain one wallet and each wallet will hold 20 film-coated tablets (i.e. seven days treatment plus three days reserve). The number of kits dispensed at each dispensing visit, will be sufficient to cover both the planned number of weeks of treatment between visits, and the use of any permitted visit windows.

For details of packaging and the description of the label, refer to the ISF.

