#### Footnotes:

- The screening period consists of 2 visits (Visits 1a/b). These visits should ideally be completed within a period of 4 weeks. There is no minimum duration. A trial participant can proceed from one visit to the next as soon as all results from the previous visit are available and if he / she remains eligible for the trial. Refer to Sections 5.1.2, 5.2.5.1, 5.2.5.2 and 6.2.1
- Visit 2 = enrolment / randomisation / Day 1 of trial medication. All assessments at this visit (excluding post-dose ECGs [refer to Sections 5.2.4, 6.2 and Appendix 10.1]) should be completed before the first dose of trial medication is administered
- 3. Trial participants who complete 8 weeks of treatment will have an End of Treatment (EoT) visit, followed 2 weeks later by an End of Study (EoS) visit. The last dose of trial medication will be administered in the evening of the day before the EoT visit. Trial participants who discontinue trial medication prematurely will have an Early Discontinuation (ED) visit completed instead of the planned treatment period visit. The ED visit should be performed within 7 days of discontinuing the trial medication, followed 2 weeks later by an EoS visit. Refer to Section 6.2.2.1 for details of assessments that should be performed during an ED visit and the EoS visit that follows it.
- 4. Fasting status: F = fasting (i.e. overnight fast, no food or drink, except water), NF = non-fasting
- 5. For further details refer to Section 6.2.1
- 6. Anthropometric measures = height (measured at Visit 1a only), weight, and waist and hip circumference. Refer to Section 5.2.1.1
- 7. Measurement of vital signs should precede the 12-lead ECG, and measurement of the 12-lead ECG should precede blood sampling and intake of trial medication at visits where a single ECG is required. The 12-lead ECG should be performed after the trial participant has rested for at least 5 minutes in a supine position. From Visit 2 onwards, the trial participants home BP monitoring equipment should be used in the clinic to measure vital signs (refer to Sections 5.2.2, 5.2.2.1 and 5.2.4)
- 8. At Visits 1a and at the EoT / ED visit, a complete physical examination is required. At all other marked visits, a physical examination is only required if the trial participant reports symptoms. Refer to Section 5.2.1

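### Two 20-tablet kits cannot cover a Visit 6 to EoT interval of 21 or 22 days, so the Section 4.1.6 supply statement fails at the edge of the visit windows (minor)

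*Protocol*

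**What the plan says.** Protocol Section 4.1.6 describes a kit as one wallet of 20 tablets, meant as a week of treatment with three further days in reserve. It adds that the number of kits dispensed at each visit "will be sufficient to cover both the planned number of weeks of treatment between visits, and the use of any permitted visit windows".

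Protocol Section 4.1.4 says participants receive "the appropriate number of medication kits for BI 685509 (range 1-2) depending on the interval between the visits". Dosing is twice daily, and "Each dose of BI 685509 will consist of one film-coated tablet".

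The Flow Chart sets Visit 6 at Day 43 ± 3 and EoT at Day 57 ± 5. SAP Table 6.7:2 gives the same limits as Days 40–46 and Days 52–62. In the Flow Chart, Visit 6 is the last visit at which drug is dispensed, and returned medication is collected at Visits 3 to 6 and at EoT. Section 6.1 counts every visit and its window from Day 1.

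On the end of dosing, Flow Chart footnote 3 says: "The last dose of trial medication will be administered in the evening of the day before the EoT visit". The second and last HVPG is scheduled at EoT.

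**The concern.** Section 4.1.6 makes an unconditional promise: whatever permitted days are used, the participant has enough tablets. The kit size and the kit limit fix the largest possible supply, and the visit windows fix the longest possible need. For one interval the need exceeds the supply, so these statements cannot all be true.

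That interval is the one that ends at the primary measurement. A participant who keeps to the windows and takes every tablet could have none left for the last one or two days before the only post-baseline HVPG. Leftover tablets are not a planned buffer, because unused drug is collected at Visit 6. An early Visit 6 does not pull EoT forward, because both are counted from Day 1. The protocol sets a minimum spacing for the titration visits but no maximum for Visit 6 to EoT.

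**Working it through.** **Inputs**
- Tablets per kit: 20 (protocol 4.1.6)
- Kits per dispensing visit: 1–2 (protocol 4.1.4)
- Tablets per day: 1 per dose × 2 doses = 2 (protocol 4.1.4)
- Visit windows: Flow Chart; SAP Table 6.7:2 for Visit 6 and EoT
- Last dose: the evening before EoT (Flow Chart footnotes 3 and 22; protocol 4.1.4)

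**Step 1: reproduce the plan's own figure.** Days per kit = 20 / 2 = 10, which matches the stated 7 + 3.

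**Step 2: largest supply at one visit.** 2 × 20 = 40 tablets; 40 / 2 = 20 days.

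**Step 3: largest need for each interval.** Longest interval = latest permitted day of the next visit − earliest permitted day of the current visit. Tablets = 2 × days, from the morning dose at the current visit to the evening before the next.

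| Interval | Longest permitted | Tablets needed | Covered by |
|---|---|---|---|
| Visit 2 to 3 | 10 − 1 = 9 days | 18 | 1 kit |
| Visit 3 to 4 | 17 − 8 = 9 days | 18 | 1 kit |
| Visit 4 to 5 | 31 − 15 = 16 days | 32 | 2 kits |
| Visit 5 to 6 | 46 − 29 = 17 days | 34 | 2 kits |
| Visit 6 to EoT | 62 − 40 = 22 days | 44 | not covered by 2 kits |

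The Flow Chart shows the Visit 5 window as +2 days. If it were ± 2, Visit 5 to 6 would need 2 × (46 − 27) = 38 tablets, still within two kits.

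The same result in days for the last interval: two kits hold 2 × 3 = 6 reserve days, while the two windows together can add 3 + 5 = 8.

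**Step 4: which day pairs fail.** There are 7 × 11 = 77 permitted pairs of Visit 6 and EoT days. A pair fails when EoT − Visit 6 exceeds 20 days.

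| Visit 6, EoT | Days | Needed | Short of 40 | Short if the Visit 6 morning dose comes from the earlier kit |
|---|---|---|---|---|
| Day 40, Day 61 | 21 | 42 | 2 | 1 |
| Day 41, Day 62 | 21 | 42 | 2 | 1 |
| Day 40, Day 62 | 22 | 44 | 4 | 3 |

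The visit-day morning dose is given at the visit, but the documents do not say which kit supplies it, so both columns are possible.

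**Step 5: timing in the worst case.** With Visit 6 on Day 40 and all doses from the new kits, 40 tablets last through the evening of Day 59. The doses of Days 60 and 61 are missing. Assuming an evening dose at 20:00 and a visit at 08:00, HVPG at EoT on Day 62 is 60 h after the last dose instead of 12 h. With the half-life of 9 to 15 h in protocol Section 1.2.1, 60 h is 60/15 = 4.0 to 60/9 = 6.7 half-lives.

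**The case against.** **Resupply is possible.** Section 6.1 lets the investigator arrange an unscheduled visit, and names supply of medication as one reason. Section 4.1.4 routes replacement kits through the IRT. A reader might infer that anyone reaching these day pairs must run out; the documents do not support that. These routes depend on someone noticing the shortage, however, and they do not make the Section 4.1.6 statement true.

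**Off-drug time before HVPG is already accepted.** Protocol Section 5.1.1 allows the EoT HVPG up to seven days after the scheduled visit. SAP Section 6.1 counts HVPG as on-treatment up to 8 days after last intake. Protocol Section 1.2.1 sets a residual effect period of 7 days. A gap of 60 h is well inside all three. A reader might infer from the half-life that the active-arm effect would be diluted by a known amount, but the documents give no relation between plasma level and HVPG. This objection stands and is the main reason the point is minor.

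**Re-titration.** Section 4.1.4.2 says that "after an interruption of trial medication of >3 consecutive doses, the trial participant should re-start the dose titration period", and a reader might infer that four missed doses trigger this rule. In the worst case the missing doses are the last ones planned, so no dosing remains to be re-started. If the earlier kit supplies the Visit 6 morning dose, only three are missed, which does not exceed the limit. The rule adds nothing to the point.

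**Frequency.** A reader might multiply 3/77 by the number of participants. That assumes uniform and independent visit days, which nothing in the documents supports, and it would count placebo participants, who cannot weaken the active-arm effect. A shortfall needs Visit 6 at least two days early and EoT at least four days late. Section 6.1 also returns later visits to the original schedule after a rescheduling, and Day 40 to the planned Day 57 is 17 days, which is covered.

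**Conclusion.** The inconsistency is certain on the documents' own figures. Two kits give 20 days, the windows permit 22, and the sufficiency statement in Section 4.1.6 is wrong for Visit 6 to EoT intervals of 21 or 22 days. The shortfall is 1–2 tablets at 21 days and 3–4 at 22 days, depending on which kit supplies the Visit 6 morning dose. It affects 3 of 77 permitted day pairs; how often these would occur in practice is unknown. The other dispensing intervals are covered.

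The result assumes that leftover drug is collected at Visit 6 as the Flow Chart marks and that no ad hoc resupply takes place. A remote Visit 6 under Section 6.2 is an exception, because medication is not collected then.

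Severity is minor. The position of the gap just before HVPG makes it worth correcting, but the accepted off-drug interval limits its weight. No trial result was affected: SAP Section 4 reports that no participant finished eight weeks and that no Week 8 HVPG was collected. The value of the correction lies in a consistent text and in any reuse of this supply plan.

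**What to change.** Reconcile three items: the kit range in protocol Section 4.1.4, the sufficiency statement in Section 4.1.6, and the Visit 6 and EoT windows in the Flow Chart and Section 6.1. The simplest route is to let the IRT dispense an additional kit at Visit 6 when EoT is booked more than 20 days later, and to widen the kit range in Section 4.1.4 accordingly. Three kits hold 60 tablets, or 30 days, which covers the 44 needed and makes the Section 4.1.6 statement true.

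The cost is one IRT setting, a small text change and an occasional extra kit. No analysis changes.
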